3.3 Strategies for Recruitment

Subjects will be recruited through a search of the dialysis unit database. Potentially eligible subjects resulting from this database search may then be approached and offered a Screening Visit if interested to participate. It is anticipated that approximately 120 potential subjects will be screened in order to enroll 25 eligible subjects, reflecting an expected screen failure rate of ~80%. 36 weeks is the anticipated timeframe for recruitment.

3.4 Subject Withdrawal or Termination

3.4.1 Reasons for Withdrawal or Termination

Upon enrollment, a subject may withdraw consent to participate in the study at any point without prejudice or consequence. Participation in this study is entirely voluntary. Likewise, a subject may also be withdrawn if the Investigator deems a subject unfit to continue with or complete the study.

Subject withdrawal or termination may occur due to any of the following reasons:

- Subject independently withdraws consent from the study
- Investigator determines that the subject has developed an intercurrent illness, condition, becomes pregnant or experiences adverse event in which continued participation in the study is considered potentially harmful to the subject and discontinuation is in the best interest of the subject
- Subject non-compliance (e.g. failure to comply with other protocol-specific assessments)
- Subject is lost to follow-up

3.4.2 Handling of Subject Withdrawals or Termination

If a subject withdraws or is discontinued from the study before completion, every effort should be made to complete the assessments. The reason for subject withdrawals from the study will be documented in the subject's case notes.

Subjects will be replaced until the targeted number of subjects has been enrolled.

4 STUDY PRODUCTS

4.1 Safe Use of Study Agent

Patiromer is an FDA-approved orally administered drug used for the treatment of hyperkalemia. It is a non-absorbed polymer that binds potassium throughout the gastrointestinal tract and leads to lowering serum potassium levels (1). Prior Patiromer clinical trials have demonstrated the drug's utility in treating hyperkalemia in patients with diabetic kidney disease (1; 2). Adverse events and other safety data will be obtained at each visit. The most commonly reported treatment related adverse events have been hypomagnesemia (7.2%), constipation (4.6%), and diarrhea (2.7%).

This study incorporates several design elements to minimize adverse events related to the study agent including:

- Eligibility criteria that exclude individuals with normal or low blood potassium levels. Only ESRD patients with hyperkalemia ($K>5.0$ mEQ/L) will be enrolled
- A maximum daily Patiromer dose of 16.8 g once daily
- Frequent monitoring of gastrointestinal symptoms
- Regular monitoring of concomitant medications and antibiotic use
- Pre-dialysis serum potassium will be monitored at regular intervals. Appropriate adjustment in dialysate potassium will be made to avoid hypokalemia.
- Follow-up of serum magnesium levels

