3.1 Inclusion Criteria

Subjects must meet all of the following criteria in order to be enrolled into the study:

1. Subjects on stable hemodialysis for more than 90 days
2. Age 18-85 years
3. Persistent hyperkalemia, defined as elevated serum potassium >5.0 mEq/L in more than 2 occasions during the previous 3 months.
4. Ability to provide informed consent

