4.2 Study Agent Dose Adjustments

4.2.1 Protocolized Dosing of Study Agent

Participants will orally self-administer Patiromer at a dose of 8.4 gram, once daily and observed for a week, during which serum potassium and gastrointestinal symptoms will be evaluated. If tolerated and in the absence of hypokalemia (serum potassium less than 4 meq/L), the dose will be up-titrated to 16.8 g once daily. Participants will remain on the 16.8 g daily dosage for another 11 weeks, for a total of 12 weeks of treatment. Study agent kits will contain 4 weeks'

worth of doses, and will be distributed three times during the course of the study. Pharmacoadherence will be ensured and confirmed through frequent communications and pill count.

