6.2.1.3 Biochemistry

Blood samples collected at weeks 0, 2, 4, 10, 14, 17, and 20 will be tested for the comprehensive metabolic panel (CMP). Blood phosphorous and PTH will be tested at week 0.

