6.3.4 Stool Sample Collection

Subjects will be provided with detailed instructions on how to collect and store their stool samples. Subjects will be instructed to collect samples from bowel movements at weeks 1, 2, 3, 4, 6, 10, 14, 17, and 20.

7 Evaluations and Follow Up

Participants will have in-person study visits at Weeks 1, 2, 3, 4, 6, 10, 14, 17 and 20. At each study visit, participants will be asked about emergency room visits, hospital admissions or any significant clinical events that occurred since the last visit. RCs will have weekly contact with participants to query them on antibiotic use in the previous week and medical records will be reviewed for blood potassium levels and antibiotics administered.

Dietary assessment using the Block Food Frequency Questionnaire (<https://nutritionquest.com>) will be administered at Baseline (W1), W8 and W20.

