7.1 Pre-Treatment Observation Phase [Week 1 and 2]

The following activities will be performed during in-person visits at weeks 1 and/or 2:

- Study Visit Assessment
- Blood Specimen Collection
- Stool Sample Collection
- Antibiotic use review
- Study medication dispensing (Week 2 only)
- Review of adverse events
- Dietary assessment using food frequency questionnaire (Week 1 only)
- Gastrointestinal symptom assessment questionnaire (Week 1 only)
- Serum Mg++ (week 2 only)

Treatment Phase [Weeks 3-14]

The following activities will be completed during in-person visits at weeks 3, 4, 6, 10 and 14:

- Study Visit Assessment
- Review of information on clinical events and current use of medications
- Blood K+ levels (weeks 3, 5, 7, 8, 9, 11, 12, and 13)

- Serum Mg++ (weeks 2, 6, 14 and 17)
- Blood Specimen Collection
- Stool Sample Collection
- Gastrointestinal symptom assessment questionnaire administration (Weeks 8 and 14)
- Review of adverse events
- Study medication dispensing (Weeks 2, 6 and 10 only)

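### The first dose has no potassium condition, so a patient already below the protocol's own 4 mEq/L definition of hypokalemia can be started on the binder (minor)

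*Combined protocol and SAP*

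**What the plan says.** Section 4.1 names several design elements meant to limit adverse events. One is "Eligibility criteria that exclude individuals with normal or low blood potassium levels", followed by a statement that enrollment is restricted to ESRD patients with K>5.0 mEq/L. Another is: "Pre-dialysis serum potassium will be monitored at regular intervals. Appropriate adjustment in dialysate potassium will be made to avoid hypokalemia".

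The criterion that decides enrollment is item 3 of section 3.1: "elevated serum potassium >5.0 mEq/L in more than 2 occasions during the previous 3 months". None of the 12 exclusions in section 3.2 concerns potassium.

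On timing, section 6.2.1.3 says "Blood samples collected at weeks 0, 2, 4, 10, 14, 17, and 20 will be tested for the comprehensive metabolic panel (CMP"), so chemistry is drawn at screening and again at week 2. Drug is first handed out in that same study week: section 7.1 lists "Study medication dispensing (Week 2 only") for the pre-treatment phase. Dedicated potassium tests come later. The treatment-phase list in section 7.1 gives "Blood K+ levels (weeks 3, 5, 7, 8, 9, 11, 12, and 13").

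On dosing, section 4.2.1 starts everyone at 8.4 g once daily. Its one numeric potassium condition applies to the next step: if the drug is tolerated and "in the absence of hypokalemia (serum potassium less than 4 meq/L), the dose will be up-titrated to 16.8 g once daily".

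Section 7 adds weekly contact with participants and says that "medical records will be reviewed for blood potassium levels and antibiotics administered". Section 3.4.1 lets the investigator withdraw a patient judged unfit to continue.

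**The concern.** Criterion 3 describes a patient's recent history. It does not describe the patient's potassium on the day treatment starts. Potassium varies from one dialysis session to the next, and two weeks of observation separate enrollment from the first dose. The plan measures chemistry at both ends of that interval but attaches no action to either result.

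The protocol therefore treats a value below 4 mEq/L as a reason not to raise the dose, but is silent on whether such a value is a reason not to begin. A patient with a week 2 potassium of, say, 3.8 can be given a drug whose purpose is to lower potassium. The next scheduled measurement is a week later. What is at stake is a small, avoidable safety risk in a trial whose primary safety endpoint is adverse events during the 12 treatment weeks.

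**Working it through.** **Text check.** The plan gives no figure on this point to reproduce. The check is whether any rule would stop a first dose when potassium is low.

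| Provision | Applies before the first dose? | Numeric threshold? | Holds the first dose? |
|---|---|---|---|
| Criterion 3 (3.1) | Yes, on values from the past 3 months | >5.0, at least 3 times | Not on a current value |
| Exclusions (3.2) | Yes | None for potassium | No |
| Week 0 and week 2 CMP (6.2.1.3) | Yes | None | No |
| Start at 8.4 g (4.2.1) | This is the first dose | None | No |
| Step to 16.8 g (4.2.1) | No, after a week on drug | <4 | No, blocks the increase only |
| Monitoring and dialysate adjustment (4.1) | Can | None | No, acts on dialysis |
| Record review (7) | Can | None | No |
| Investigator withdrawal (3.4.1) | Can | None | Only by judgment |

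No row supplies a first-dose hold. One assumption is that the CMP includes potassium, since the documents do not list its components. The schedule supports this: the dedicated potassium weeks in section 7.1 (3, 5, 7, 8, 9, 11, 12, 13) share no week with the CMP weeks (0, 2, 4, 10, 14, 17, 20). If the CMP did not include potassium, there would be no scheduled pre-dose value at all and the gap would be wider.

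**How often it could matter.** All inputs here are assumed. Let a patient's mean potassium be m ~ Normal(μ, between-patient SD), with each value equal to m plus independent Normal error (within-patient SD σ). With k look-back values, the patient is eligible if at least 3 exceed 5.0:

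- e(m) = P[Binomial(k, 1 − Φ((5.0 − m)/σ)) ≥ 3]
- p = average of e(m)·Φ((4.0 − m)/σ) over m, divided by the average of e(m)
- Expected number among 25 = 25p; chance of at least one = 1 − (1 − p)^25

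*Main set:* μ = 4.8, 5.0, 5.2; between-patient SD 0.35, 0.5; σ = 0.4, 0.5 (12 settings).

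- k = 3: p = 0.08% to 1.51%. The upper end gives 25 × 0.0151 = 0.38 and 1 − 0.9849^25 = 32%. The lower end gives 0.02 and 2%.
- k = 6: p = 0.27% to 2.78%, or 0.07 to 0.70 of 25, with a 6% to 51% chance of at least one. More look-back values make criterion 3 easier to meet.

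*Wider set:* μ = 4.8, 5.1, 5.4; between-patient SD 0.4; σ = 0.4, 0.5, 0.6.

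- Upper end (μ = 4.8, σ = 0.6, k = 6): p = 5.2%, so 25 × 0.052 = 1.3 and 1 − 0.948^25 = 74%.
- Lower end (μ = 5.4, σ = 0.4, k = 3): p = 0.04%, so 25 × 0.0004 = 0.01 and about a 1% chance of any.

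The result depends mainly on the within-patient SD and the number of look-back values, and the documents give neither.

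**The case against.** The case for leaving the plan alone has real force.

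- *A reader might infer that section 4.1 contradicts section 3.1.* The documents do not support that. Section 4.1 goes on to say that only patients with K>5.0 will be enrolled, and criterion 3 is a reasonable way to implement that statement. Someone with at least three values above 5.0 in three months does not ordinarily have normal or low potassium. Section 4.1 is best read as a summary of 3.1.
- *A reader might infer that 4.0 is a general dosing limit which the plan then breaks.* It is not. In 4.2.1 it bars the increase to 16.8 g, and nothing tells a patient already on 8.4 g to stop below 4. Using 4.0 as a condition for starting extends the protocol's definition. It also leaves an asymmetry: a patient at 3.9 before treatment would wait, while one at 3.9 on treatment may continue.
- *A reader might infer that patients are unprotected, or protected only by discretion.* Monitoring, record review and dialysate adjustment are all stated as things that will be done. Only withdrawal is worded as optional. Dialysate adjustment acts directly on the hazard and can act before dosing.
- *A reader might treat any week 2 value at or below 5.0 as a failure.* In the main set with k = 3, that would be 12% to 35% of patients (3 to 9 of 25). Much of this is ordinary fluctuation and is not a safety problem.

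The drug is also approved, is started at its lower dose, and potassium is rechecked after a week. All this limits the weight of the point. It does not fill the gap: none of these provisions holds a first dose on a low result.

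**Conclusion.** The point stands as a minor one. Criterion 3 establishes persistent hyperkalemia from past values, section 4.2.1 starts treatment with no potassium condition, and the definition of hypokalemia at below 4 mEq/L comes into play only at the dose increase. A patient who meets that definition at week 2 can be started under the plan as written.

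That part rests on the text alone. The expected frequency, about 0.02 to 1.3 of 25 patients (0.01 at the single most favorable setting tried), rests wholly on assumed means and SDs and on independent errors. It shows that the event is probably rare, and should not be read as an estimate for this trial.

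**What to change.** Add to section 4.2.1: the first dose waits for the week 2 pre-dialysis potassium and is withheld if that value is below 4.0 mEq/L. Repeat the test once. If the repeat is 4.0 or above, start treatment; otherwise do not start, and replace the patient under section 3.4.2. For a delayed start, count the 12 treatment weeks, and the on-treatment visits, kits and stool and blood samples, from the actual first dose. Without that last sentence, a held patient's microbiome and metabolome samples would fall at the wrong time on treatment.

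The cost is a short wait for a result before each of the 25 first doses, plus a moved schedule for the rare held patient. The rule uses a sample already planned and adds no screen failures. Only a patient with two values below 4.0 would never start. In the main set that is at most 0.07% of eligible patients with 3 look-back values and 0.18% with 6, and it would be higher if within-patient variation were larger.

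A stricter gate requiring K>5.0 at week 0 is not worth adding. In the main set with 3 look-back values it spares only 0.6 to 1.2 of 25 patients a week 2 value at or below 5.0, for 17 to 64 extra patients screened beyond the planned 120 or so.

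Optionally, reword the eligibility item in section 4.1 to refer to persistent hyperkalemia in the previous 3 months, so that it says no more than criterion 3 delivers.

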4.2 Study Agent Dose Adjustments

4.2.1 Protocolized Dosing of Study Agent

Participants will orally self-administer Patiromer at a dose of 8.4 gram, once daily and observed for a week, during which serum potassium and gastrointestinal symptoms will be evaluated. If tolerated and in the absence of hypokalemia (serum potassium less than 4 meq/L), the dose will be up-titrated to 16.8 g once daily. Participants will remain on the 16.8 g daily dosage for another 11 weeks, for a total of 12 weeks of treatment. Study agent kits will contain 4 weeks'

worth of doses, and will be distributed three times during the course of the study. Pharmacoadherence will be ensured and confirmed through frequent communications and pill count.

5 ADVERSE EVENTS

This section describes the requirements and processes for reporting adverse events and unanticipated problems that occur during the study to Relypsa and the IRB.

5.1 Definitions

Definitions are per the January 2007 Guidance on Reviewing and Reporting Unanticipated Problems Involving Risks to Participants or Others and Adverse Events, Office on Human Research Protection (OHRP) Guidance. <http://www.hhs.gov/ohrp/policy/AdvEvntGuid.htm>. The requirements and processes for reporting adverse events are described in the corresponding NIH Guidelines.

Adverse Event (AE): An AE is any untoward or unfavorable medical occurrence in a human study participant, including any abnormal sign (for example, abnormal physical exam or laboratory finding), symptom, or disease, temporally associated with the participant's involvement in the research, whether or not considered related to the participant's participation in the research.

Internal adverse event: From the perspective of one particular institution engaged in a multicenter clinical trial, internal adverse events are those adverse events experienced by participants enrolled by the investigator(s) at that institution.

5.2 Collecting Adverse Event Information

The Investigator and research team is obligated to monitor participants so that their participation in the clinical trial is as safe as possible.

The center staff will collect adverse event data at each study visit by checking several different sources of information by:

- asking participants directly
- evaluating medical record information
- reviewing all laboratory values
- examining reports generated by the data management system based on data entered into logs and forms

AE information may also be reported between scheduled study visits via regular contacts if the participant reports health related problems or concerns. The study period during which adverse events must be reported is defined as the period from initiation of the study procedures to the end of the treatment follow-up. In other words, AE documentation should begin when the patient signs the informed consent form.

Encourage participants to contact the investigator after the conclusion of the trial if subsequent medical events occur which the participant, or the participant's physician, believes may be related to participation in the research study.

Other medical information

A participant may report that he or she had a medical test or procedure. If so, inquire as to why this was done as it may reveal pertinent information about a medical condition or diagnosis. In addition, if a participant reports starting a new medication, it may also indicate a new diagnosis or a change in a pre-existing medical condition that should be discussed and documented on the AE form.

5.2.1.1 Serious Adverse Events

A Serious Adverse Event (**SAE**) is defined as any AE that results in any of the following outcomes:

- fatal
- life-threatening
- requires or prolongs hospital stay
- results in persistent or significant disability or incapacity
- results in congenital anomalies or birth defects
- an important medical event

Important medical events are those that may not be immediately life threatening, but are clearly of major clinical significance. SAE reporting requirements are based on meeting the outcome definition outlined above.

Note that for this trial, hospitalized is defined as staying overnight in the hospital. Time spent in the emergency department may or may not be reported as an SAE, depending on the reason for the ED visit.

5.3 Reporting Adverse Events and Serious Adverse Events

The Investigator must report all SAEs from the signing of the informed consent until 14 days after the last dose of Patiromer to Relypsa's Drug Safety and Pharmacovigilance (DSPV) Department within 24 hours of becoming aware. SAE follow up information must also be provided as requested by Relypsa.

All SAE reports will be sent to Relypsa's Drug Safety by email to [contact] or via fax to [contact]. The Relypsa Generic IST SAE Form will be used for reporting SAEs to Relypsa's DSPV Department. All pertinent SAE information as indicated on the reporting form or as requested by Relypsa will be provided to facilitate safety monitoring for all patients taking Patiromer. These reports will be submitted by the Investigator or the research team to Relypsa even if it is not felt to be drug related. Prior to the start of the study, the Investigator and research team will complete SAE reporting training provided by Relypsa and document completion of the training.

The research team will also report any pregnancy that occurs in a female study patient or the male participant's female partner or any lactation exposure occurring to an infant or child by a female study patient within 24 hours of becoming aware to Relypsa's Drug Safety by email or fax. All pregnancy or lactation exposures will be reported on the Relypsa Generic IST Pregnancy or Lactation Report Form.

6 STUDY PROCEDURES AND SCHEDULE

6.1 Study Procedures/Evaluations

6.1.1 Study Specific Assessments and Procedures

This section describes the study specific assessments and procedures that will be conducted. Results from study specific procedures (e.g., laboratory evaluations or questionnaire results) will not be provided to subjects, unless the results are necessary in order to effectively communicate follow-up care for any adverse events that may occur as a result of participating in the study.

[figure not shown]

Figure 1. Sample collection. Stool and blood samples will be collected at weeks 1, 2, 3, 4, 6, 10, 14, 17 and 20 of the study. We will obtain information regarding dietary pattern and gastrointestinal health. Adverse events related to study drugs, and clinical events will also be collected. Patients will be requested to complete gastrointestinal (GI) health assessment survey at baseline, during treatment, and during post-treatment phase. Detailed information about infection and type of antibiotic used (if any) will be collected.

6.1.1.1 Medical History

A detailed medical history will be obtained. Subject's medical history will be obtained by chart review and interview.

6.1.1.2 Medication History

Subject's medication history will be obtained during each visit, including prescription, over-the-counter medications, and dietary supplements.

6.1.1.3 Dietary Assessment

Dietary assessment using the Block Food Frequency Questionnaire (<https://nutritionquest.com>) will be administered at the beginning (Week 1), during (Week 8) and end of the study (Week 20).

6.1.1.4 Physical Examination

A physical examination will be conducted, which will include body measurements (including height, weight, and calculation of BMI) and an assessment of vital signs (blood pressure, pulse, body temperature).

6.1.1.5 Biological Specimen Collection and Laboratory Evaluations

Stool and blood specimens will be collected from all subjects. In addition, data from routine laboratory investigations required for standard of care will be included into the clinical database as deemed necessary for annotation of the stool samples to the course of clinical disease and treatment.

6.1.2 Standard of Care Study Procedures

All subjects for this study are receiving the study specific assessments solely due to study participation. Therefore, there are no applicable standard of care procedures associated with this study.

6.2 Laboratory Procedures/Evaluations

6.2.1 Clinical Laboratory Evaluations

6.2.1.1 Serum Pregnancy Test

A serum/urine pregnancy test will be conducted at the Screening Visit for women of childbearing potential.

6.2.1.2 Hematology

Blood samples collected at weeks 0, 2, 4, 10, 14, 17, and 20 will be tested for CBC.

6.2.1.3 Biochemistry

Blood samples collected at weeks 0, 2, 4, 10, 14, 17, and 20 will be tested for the comprehensive metabolic panel (CMP). Blood phosphorous and PTH will be tested at week 0.

